### **2.2.1 Randomization and drug dispensing irregularities**

Randomization and drug-dispensing irregularities occur whenever:

1. A randomization is not in accordance with the protocol-defined randomization method, such as
    - a) an ineligible patient is randomized,
    - b) a patient is randomized based on an incorrect stratum,
    - c) a patient is randomized twice.
- OR
2. A patient is dispensed an IMP kit not allocated by the protocol-defined randomization, such as
    - a) a patient at any time in the study is dispensed a different treatment kit than as randomized (which may or may not contain the correct-as-randomized IMP), or
    - b) a non-randomized patient is treated with IMP reserved for randomized patients.

Randomization and drug-dispensing irregularities will be monitored throughout the study and reviewed on an ongoing basis.

All randomization and drug-dispensing irregularities will be documented in the clinical study report. If the number of irregularities is large enough to make a tabular summary useful, the irregularities will be categorized and summarized among randomized patients (number and percentages). Non-randomized, treated patients will be described separately.

Randomization and drug-dispensing irregularities to be prospectively identified include but are not limited to:

Randomization and drug allocation irregularities
Kit dispensation without IRT transaction
Erroneous kit dispensation
Kit not available
Randomization by error
Patient randomized twice
Stratification error
Patient switched to another site

## **2.3 ANALYSIS POPULATIONS**

Patients treated without or before being randomized will not be considered randomized and will not be included in any analysis population. The safety experience of these patients will be reported separately.

The randomized population includes any patient who has been allocated to a randomized treatment regardless of whether the treatment kit was used.

For any patient randomized more than once, only the data associated with the first randomization will be used in any analysis population. The safety experience associated with any later randomization will be assessed separately.

### **2.3.1 Efficacy populations**

#### **2.3.1.1 Modified intent-to-treat population**

The modified intent-to-treat (mITT) population is defined as all randomized patients who received at least 1 dose or part of a dose of the IMP. Patients in the mITT population will be analyzed according to the treatment arm to which they are randomized.

#### **2.3.2 Safety population**

The safety population is defined as randomized population who actually received at least 1 dose or part of a dose of the IMP, analyzed according to the treatment actually received.

In addition:

- Non-randomized but treated patients will not be part of the safety population; however, their safety data will be presented separately
- Randomized patients for whom it is unclear whether they took the IMP will be included in the safety population as randomized
- For patients receiving more than 1 IMP during the trial, the treatment arm allocation for as-treated analysis will be the one received at the majority of injections during the first 52 weeks of treatment in terms of kits.

### **2.3.3 Pharmacokinetics population**

The PK analysis will be performed on all randomized and treated patients (safety population) with at least one available PK sample post first double-blind IMP injection.

### **2.3.4 Immunogenicity population**

The anti-SAR156597 antibody analysis will be performed on all randomized and treated patients (safety population) with at least one available ADA sample post first double-blind IMP injection.

### **2.3.5 Biomarker population**

Baseline biomarker population includes the randomized and treated patients with a baseline sample successfully analyzed.

Pharmacodynamics biomarker population includes the randomized and treated patients with a baseline sample and at least one post first double-blind IMP injection sample successfully analyzed.

## **2.4 STATISTICAL METHODS**

Continuous data will be summarized using the number of available data, mean, standard deviation (SD), median, minimum and maximum for each treatment arm. Categorical and ordinal data will be summarized using the number and percentage of patients in each treatment arm.

### **2.4.1 Demographics and baseline characteristics**

Parameters will be summarized on the randomized population analyzed in the treatment arm to which they were randomized and according to background therapy status.

Parameters described in [Section 2.1.1](#) will be summarized by treatment arm and overall treatment groups using descriptive statistics.

Medical/surgical history will be summarized in each treatment arm by primary SOC, HLT and PT. Events will be sorted by SOC internationally agreed order and decreasing frequency of PT based on the incidence in the overall treatment arm.

P-values on demographic and baseline characteristic data will not be calculated.

A specific quantitative description of the efficacy parameters will be provided at baseline by treatment arm and by background therapy status. In particular, Q1 and Q3 will be described for PFTs. In addition, the terciles categories at baseline will be displayed for % predicted FVC and % predicted DLCO parameters.

#### **2.4.2 Prior or concomitant medications**

Specific prior medications (Nintedanib, Pirfenidone, Systemic Corticosteroids, N-Acetylcysteine, Anti-acid (including PPI and H2 receptor blocker)) and other prior medications will be presented separately for the randomized population.

Specific concomitant medications (Nintedanib, Pirfenidone, Systemic Corticosteroids, N-Acetylcysteine, Anti-acid (including PPI and H2 receptor blocker)) and other concomitant medications will be presented separately for the randomized population.

Specific post-treatment medications (Nintedanib, Pirfenidone, Systemic Corticosteroids, N-Acetylcysteine, Anti-acid (including PPI and H2 receptor blocker)) and other concomitant medications will be presented separately for the randomized population.

Specific prior, concomitant, post-treatment medications will be summarized by treatment arm according to the WHO-DD dictionary, considering the first digit of the anatomic category (ATC) class (anatomic category) and standardized medication names.

Other prior, concomitant, post-treatment medications will be summarized by treatment arm according to the WHO-DD dictionary, considering the first digit of the anatomic category (ATC) class (anatomic category) and the first 3 digits of the ATC class (therapeutic category). All ATC codes corresponding to a medication will be summarized, and patients will be counted once in each ATC category (anatomic or therapeutic) linked to the medication. Therefore patients may be counted several times for the same medication.

The table for prior specific medications will be sorted by decreasing frequency of ATC followed by the standardized medication names based on the overall incidence across treatment groups. The table for other prior medications will be sorted by decreasing frequency of ATC followed by all other therapeutic classes based on the overall incidence across treatment groups. In case of equal frequency regarding ATCs (anatomic or therapeutic categories or standardized medication names), alphabetical order will be used.

The tables for specific concomitant and post-treatment medications will be sorted by decreasing frequency of ATC followed by standardized medication names based on the incidence on the column all. The tables for other concomitant and post-treatment medications will be sorted by decreasing frequency of ATC followed by all other therapeutic classes based on the incidence on

the column all. In case of equal frequency regarding ATCs (anatomic or therapeutic categories or standardized medication names), alphabetical order will be used.

In addition, the following specific medications will be summarized on the randomized population:

- The prohibited medications will be presented in the deviations table.
- For the specific concomitant medications (Pirfenidone, Nintedanib, Systemic Corticosteroids, NAC and Anti-acid therapy (combined anti-acid, PPI and H2 receptor blocker)), the number of patients taking at least one dose at randomization will be summarized. For Pirfenidone, Nintedanib and Systemic Corticosteroids only, the mean, median, standard deviation (SD), minimum and maximum dose will be summarized (use of the standard prednisone equivalent dose for Systemic Corticosteroids). If several doses for a given medication were taken by patient at this timepoint, the sum of the doses will be used.
- The change in dose for Nintedanib and Pirfenidone medications will be described by visit and treatment arm according to the “Status of IPF Background Therapy” eCRF page: Has the dose of the background therapy changed since the previous visit? (Yes, No).

A list of ATC codes to be used in determining these specific medications is displayed in [Appendix F](#).

### **2.4.3 Extent of investigational medicinal product exposure and compliance**

The extent of IMP exposure and compliance will be assessed and summarized by actual treatment within the safety population ([Section 2.3.2](#)).

#### **2.4.3.1 Extent of investigational medicinal product exposure**

The extent of IMP exposure will be assessed by the duration of IMP exposure.

Duration of IMP exposure is defined as last dose date – first dose date + 7 days, regardless of unplanned intermittent discontinuations (see [Section 2.5.3](#) for calculation in case of missing or incomplete data).

Duration of IMP exposure will be summarized descriptively as a quantitative variable (number, mean, SD, median, minimum, and maximum) in weeks. In addition, duration of treatment exposure will also be summarized categorically by numbers and percentages for each of the following categories and cumulatively according to these categories:  $\geq 1$  day and  $< 2$  weeks,  $\geq 2$  weeks and  $< 4$  weeks,  $\geq 4$  weeks and  $< 6$  weeks,  $\geq 6$  weeks and  $< 12$  weeks,  $\geq 12$  weeks and  $< 24$  weeks,  $\geq 24$  weeks and  $< 36$  weeks,  $\geq 36$  weeks and  $< 44$  weeks,  $\geq 44$  weeks and  $< 53$  weeks and  $\geq 53$  weeks. Non-integer values will be rounded to 1 decimal place.

Additionally, the cumulative duration of treatment exposure will be provided, defined as the sum of the duration of treatment exposure for all patients, and will be expressed in patient years.

The graphical representation of exposure to investigational product and time since randomization will also be displayed by treatment arm.

### **2.4.3.2 Compliance**

A given administration will be considered noncompliant if the patient did not take the planned dose of treatment as required by the protocol. No imputation will be made for patients with missing or incomplete data.

**Overall percentage of compliance** for a patient will be defined as  $100 - (\% \text{ day with below-planned dosing} + \% \text{ days with above-planned dosing})$ , considering that injection should be performed every week  $\pm 2$  days as per protocol.

**Above-planned dosing percentage** for a patient will be defined as the number of days with more than 1 injection administration within the 5 days before divided by the duration of IMP injection exposure in days.

**Below-planned dosing percentage** for a patient will be defined as the number of days with no injection administration within the previous 9 days divided by the duration of IMP injection exposure in days.

These parameters will be summarized descriptively as quantitative variables (number, mean, SD, median, minimum, and maximum).

The overall percentage of patients whose compliance is  $\geq 80\%$  will be summarized. In addition, numbers and percentages of patients with  $>0$  and  $\leq 5$ ,  $>5$  and  $\leq 10$ ,  $>10$  and  $\leq 20$  and  $>20\%$  days with above-planned dose administrations will also be provided, as well as numbers and percentages of patients with  $>0$  and  $\leq 5$ ,  $>5$  and  $\leq 10$ ,  $>10$  and  $\leq 20$  and  $>20\%$  days with below-planned dose administrations.

In addition, the following parameters will be summarized by treatment arm:

- The number of IMP injections (mean (SD), median, Min:Max description).
- The number of advanced injections (less than 5 days between two consecutive injections) and the number of delayed injections (more than 9 days between two consecutive injections).
- The number of patients with at least one advanced injection and the number of patients with at least one delayed injection. A patient could be counted in several categories.
- The frequency of IMP injections (mean (SD), median, Min:Max description) will be defined for each patient as the average number of days between two consecutive injections:  $(\text{last injection date} - \text{first injection date}) / (\text{number of injections} - 1)$  for patients with at least 2 injections.

Cases of overdose are reported in the AE e-CRF pages as AESI if symptomatic or AE if asymptomatic. The reported cases of overdose will be described in the AE analysis (see [Section 2.1.4](#) and [Section 2.4.5.1](#)).

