The IMP is administered every 7 days +/- 2 days from initial IMP administration. This is permitted per protocol to accommodate special circumstances, eg. laboratory results pending, ongoing AE, patient scheduling difficulty.

If IMP administration is missed or temporarily discontinued, the initial schedule of injections should be resumed. This does not apply to permanent treatment discontinuation.

On days when the patient has a study visit, the IMP will be administered by the Investigator or delegate after clinic procedures and blood collection.

For doses not administered at the study site, the IMP will be administered by qualified site personnel and /or healthcare professionals (e.g. visiting nurse service).

Patients should be monitored by site personnel/visiting nurse for at least 30 minutes after each administration for potential signs and symptoms that may suggest a hypersensitivity reaction.

[For Czech Republic only per local requirement: Patients should be monitored at the study site by site personnel for a minimum of 2 hours after the first administration of IMP and for a minimum of 1 hour after the next 5 administrations for potential signs and symptoms that may suggest a hypersensitivity reaction. For the subsequent IMP administrations, patients should be monitored by site personnel/visiting nurse for at least 30 minutes after each administration.]

For doses not given at study site, a booklet will be provided to the patient to record information related to the injections; this booklet will be completed by the visiting nurse after each injection and will be kept as source data in the patient's study file. Patients will be instructed to bring the booklet back at the subsequent site visit for Investigator's review.

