11.4.1.2 Compliance

A given administration will be considered noncompliant if the patient did not take the planned dose of treatment as required by the protocol. No imputation will be made for patients with missing or incomplete data.

Treatment compliance, above-planned and under-planned dosing percentages will be summarized descriptively (N, Mean, SD, Median, Min, and Max). The percentage of patients with compliance <80% will be summarized. In addition, number and percentage of patients with at least 1 above-planned dosing administration will be given, as well as the number and percentage of patients with 0, (0, 20%), and >20% under-planned dosing administrations.

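### Compliance is computed per day rather than per dose, so the percentage overstates injections received and does not separate active from placebo doses in the q2w arm

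*SAP*

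**What the plan says.** SAP 2.4.3.2 starts from the dose: "A given administration will be considered noncompliant if the patient did not take the planned dose of treatment as required by the protocol". It then sets overall compliance at 100 minus two percentages of days, "considering that injection should be performed every week" within 2 days either way. The below-planned percentage is the "number of days with no injection administration within the previous 9 days divided by the duration of IMP injection exposure in days". The above-planned percentage is the "number of days with more than 1 injection administration within the 5 days before divided by the duration of IMP injection exposure in days". The share of patients at 80% or more is then summarised. Protocol 11.4.1.2 planned the complementary figure ("The percentage of patients with compliance <80% will be summarized") and banded patients by under-planned administrations, not days.

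The denominator in SAP 2.4.3.1 is last dose minus first dose plus 7 days, "regardless of unplanned intermittent discontinuations". SAP 1.5 records the change in the exposure definition but not the move from administrations to days.

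Protocol 8.1 gives the dosing rule: "The IMP is administered every 7 days +/- 2 days from initial IMP administration". After a miss, "If IMP administration is missed or temporarily discontinued, the initial schedule of injections should be resumed". In the q2w arm, active and placebo injections alternate weekly.

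**The concern.** A compliance percentage is normally read as the share of planned doses received. Here the numerator counts days lying beyond a tolerated gap, so each missed dose is charged less than the week it covers, and steady slow dosing may be charged nothing.

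Two further mismatches follow. The formula scores any injection alike, although half of the q2w arm's injections are placebo. And the 5-day and 9-day limits apply to the gap between consecutive injections, whereas the protocol window is fixed to the first dose. Successive doses within 2 days of their scheduled day can be 3 to 11 days apart.

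The trial compares two dosing frequencies, and its Week 52 results feed the Phase 3 decision (SAP 1.5). Readers will want to know how much of each regimen was delivered.

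**Working it through.** The documents give no compliance result to reproduce. I applied the formula day by day to injection calendars.

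**Inputs**
- Dosing from Day 1 to Week 52 (SAP 1.4): 53 weekly injections.
- Exposure (SAP 2.4.3.1): 364 + 7 = 371 days.
- q2w arm: 27 active and 26 placebo injections, assuming the first is active. The other order gives 26 active.
- The SAP does not say whether the current day counts. Three readings of the 9-day look-back (d-9 to d, d-9 to d-1, d-8 to d) were crossed with three of the 5-day look-back (d-5 to d, d-5 to d-1, d-4 to d).
- Check: exact weekly dosing gives 100% under all nine.

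**Charge for one missed dose.** The schedule is kept, so the gap runs from day 0 to day 14. Uncovered days are 10 to 13 (4 days), or 10 to 14 or 9 to 13 (5 days).

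**Doses missed regularly**

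| Pattern | Injections received | Below-planned days | Computed compliance |
|---|---|---|---|
| Every 4th missed (13) | 40/53 = 75.5% | 13×4 = 52 to 13×5 = 65 of 371 | 86.0% to 82.5% |
| Every 3rd missed (17) | 36/53 = 67.9% | 17×4 = 68 to 17×5 = 85 of 371 | 81.7% to 77.1% |
| One every 9 days | 41/53 = 77.4% | 0 | 100% |

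**q2w arm.** If the 13 misses in the first row are all active doses (Weeks 2, 6, …, 50) and every placebo is taken, active doses received are 14/27 = 51.9%. The score is still 82.5% to 86.0%. If active doses stop after Week 26 and placebo continues to Week 51, there are 12 gaps: 48 to 60 of 364 days, or 86.8% to 83.5%.

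**All 53 injections inside the anchored window, alternating +2 and -2 days.** Exposure is 362 + 7 = 369 days, with 25 gaps of 11 days and 26 gaps of 3 days.
- Below-planned: 25×1 to 25×2 = 25 to 50 days (6.8% to 13.6%).
- Above-planned: 26×2 to 26×3 = 52 to 78 days (14.1% to 21.1%).
- Compliance: 100 - 100×(25+52)/369 = 79.1% down to 100 - 100×(50+78)/369 = 65.3%.

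The 9-day term alone would leave 86.4% to 93.2%, so most of the loss comes from the 5-day term.

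**Milder in-window patterns.** Alternating +2/-1 gives 79.2% to 93.0%, dipping under 80% only with the strictest day counts. Alternating +1/-1 gives 93.0% to 100%. With each injection placed at random from -2 to +2 days (1,000 simulated patients per day count), mean compliance was 92% to 97%, the lowest value was about 85%, and none fell below 80%.

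**The case against.** Four objections carry weight.

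- **Other summaries show under-dosing.** SAP 2.4.3.2 also tabulates injection counts, delayed injections, the mean interval and bands of below-planned days. The patient missing every 4th dose would show 40 injections, 13 delayed injections, a mean interval of 364/39 = 9.3 days and the band above 10% and up to 20%. SAP 2.4.6 reports trough concentrations by arm and time point. A reader might infer that a weak q2w result could not be told apart from under-dosing. The documents do not support that. But none of the exposure and compliance summaries separates active from placebo, and troughs at a few visits do not count doses.
- **The 14-of-27 case is extreme.** Patients and investigators are blinded. If 13 of 53 misses fell at random, the chance that all were active is C(27,13)/C(53,13), about 2 in 100,000, and about 27×40/53 = 20 active doses would be expected. The case shows what the formula cannot detect, not what is likely.
- **The sub-80% case is also extreme.** A reader might infer that patients who follow the protocol will often be flagged, or that the 9-day rule is to blame. Neither holds. If the window is read as 5 to 9 days between injections, alternating 5- and 9-day gaps give 93.0% to 100% and constant 5-day gaps 80.5% to 100%.
- **No efficacy analysis depends on it.** There is no per-protocol population, and the primary analysis uses mITT regardless of treatment discontinuation.

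These limit the consequence. They do not remove the gap between the reported percentage and the doses received.

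**Conclusion.** The point holds as a correction to a descriptive summary and should be made. Charging 4 to 5 days per missed weekly dose lifts 75% of injections received to 82–86% and 68% to 77–82%; dosing every 9 days is not charged at all. The first of these moves a patient across the 80% line under every day count tried. This conflicts with the section's own per-administration definition and with Protocol 11.4.1.2.

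The lack of an active-dose count in q2w is a real gap, but its extreme illustration assumes that only active doses are missed. The window mismatch can penalise fully in-window dosing. Only the sustained +2/-2 pattern fell below 80% under every reading (65–79%), and this relies on reading Protocol 8.1 as anchored to the first dose.

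The effect is on how exposure is interpreted. The primary test and the analysis populations are untouched.

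**What to change.** In SAP 2.4.3.2:

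1. Define compliance as injections received divided by injections scheduled between first and last dose, and apply the 80% cut to that ratio.
2. For the q2w arm, also report active injections received divided by active injections scheduled. Derive this from the kit records (Protocol 8.7.1) and the Box 1/Box 2 week (Protocol 8.3.1). The documents do not show that the box used is captured in the e-CRF, so confirm this or derive it from kit number and week.
3. Report early and late injections separately, against the scheduled day in Protocol 8.1 rather than the previous injection. A late dose should not count as missed, or the ratio would measure punctuality rather than drug received.
4. List the change in SAP 1.5.

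The cost is SAP wording and a simpler derivation from injection dates and kit records. Efficacy analyses are unchanged. The reported percentage compliant may be less favourable.

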## 2.4.4 Analyses of efficacy endpoints

All visits will be re-allocated as given in [Table 6](#), and re-allocated visits measurements will be included in the by-time point summaries unless otherwise specified.

